9.4.3. Other Events that Require Accelerated Reporting to Sponsor

The following events also require reporting to the sponsor (or designee) within 24 hours of learning of the event:

Symptomatic Overdose of Study Drug: Accidental or intentional overdose of at least 2 times the intended dose of study drug within the intended therapeutic window, if associated with an AE,

Pregnancy: Although pregnancy is not considered an AE, it is the responsibility of the investigator to report to the sponsor (or designee), within 24 hours of identification, any pregnancy occurring in a female patient or female partner of a male patient, during the study or within 24 weeks of the last dose of study drug. Any complication of pregnancy affecting a female study patient or female partner of a male study patient, and/or fetus and/or newborn that meets the SAE criteria must be reported as an SAE. Outcome for all pregnancies should be reported to the sponsor.

Adverse Events of Special Interest: All AESI, serious and nonserious, must be reported within 24 hours of identification using the same reporting process as for SAE reporting, per Section 9.4.2.

Adverse events of special interest for evinacumab include the following:

- Anaphylactic reactions
- Moderate or severe infusion reactions

- Increase in ALT or AST: ≥ 3 x ULN (if baseline <ULN), or ≥ 2 times the baseline value (if baseline \geq ULN)
- Allergic events and/or local injection site reactions that require medical treatment or that require consultation with another physician for further evaluation
- Pregnancy
- Symptomatic overdose with investigational medicinal product
- Neurocognitive events
- New onset of diabetes*
- Pancreatitis

Adverse events of special interest for alirocumab include the following:

- Increase in ALT: ALT ≥ 3 x ULN (if baseline ALT <ULN), or ALT ≥ 2 times the baseline value (if baseline ALT \geq ULN)
- Allergic events and/or local injection site reactions that require consultation with another physician for further evaluation
- Pregnancy
- Symptomatic overdose with investigational medicinal product
- Neurologic events that require additional examinations/procedures and/or referral to a specialist
- Neurocognitive events
- Cataracts
- New onset of diabetes*

*New onset of diabetes is defined as any of the following:

- Type 1 or type 2 diabetes TEAE (grouping of MedDRA terms will be specified in the statistical analysis plan [SAP])

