- At least 2 HbA1c measurements $\geq 6.5\%$ during the TEAE period (NOTE: For patients with only a single measurement available during the TEAE period, a single value $\geq 6.5\%$ will qualify the patient as NOD by default)
- At least 2 fasting glucose measurements ≥ 126 mg/dL (7.0 mmol/L). For patients with several fasting glucose measurements but with only the last one ≥ 126 mg/dL (7.0 mmol/L), this single value ≥ 126 mg/dL (7.0 mmol/L) will NOT be considered and will NOT qualify the patient as NOD)

Refer to the study manual for the procedures to be followed.

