1.2.3. Modifications from the Statistical Section in the Final Protocol

N/A.

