New onset of diabetes (NOD) for patients without diabetes mellitus at baseline	No	
No medical history of diabetes as specified in Cardiovascular History and Cardiovascular Risk Factors and Medical History CRF pages, AND Hb1Ac < 6.5% at baseline
 
AND one of the following:
 
Lab criteria: At least 2 values of HbA1c \geq6.5% during the TEAE period. NOTE: For patients with only a single measurement available during the TEAE period, a single value \geq6.5% will be considered and qualify the patient as NOD by default. For patients with several HbA1c measurements but only with the last one \geq6.5%, this single value \geq6.5% will be considered and qualify the patient as NOD by default.
 
OR
 
Lab criteria: At least 2 values of fasting glucose \geq126 mg/dL (7.0 mmol/L). NOTE: For patients with only a single measurement available during the TEAE period, a single value \geq126 mg/dL (7.0 mmol/L) will NOT be considered and will NOT qualify the patient as NOD. For patients with several fasting glucose measurements but only with the last one \geq126 mg/dL (7.0 mmol/L), this single value \geq 126 mg/dL (7.0 mmol/L) will NOT be considered and will NOT qualify the patient as NOD.
 
OR
 
HLT Diabetes mellitus (including subtypes)
 
OR
 
- Initiation of any new concomitant medication for hyperglycemia during the treatment period

Diabetic complication for patients with diabetes mellitus at baseline	No	For patients with medical history of diabetes as specified in Cardiovascular History and Cardiovascular Risk Factors and Medical History CRF pages, each of the following criteria will be considered, respectively:

AESI	Using an e-CRF specific tick box on AE page	Using Standard MedDRA Query (SMQ)/company MedDRA Query (CMQ) or lab data
		
 • Diabetes mellitus or diabetic complication TEAEs using HLTG Diabetic complications, HLT Diabetes mellitus (incl subtypes), and PTs Blood glucose increases, Glycosylated haemoglobin increased, Hyperglycaemia, Hyperglycaemic unconsciousness, and Hyperglycaemic seizure • Changes in diabetic medication dosage (specifically increases in dosage) or initiation of additional diabetic medication
Pancreatitis	Yes	No
Cataracts	No	HLT Cataract conditions
Immune complex diseases	No	SMQ (Narrow) Systemic lupus erythematosus SMQ (Narrow) Vasculitis SMQ (Narrow) Guillain-Barre syndrome

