10.4. Criteria for Potentially Clinically Significant Values (PCSV)

Parameter	PCSV
Clinical chemistry	
ALT	By distribution analysis: >2 ULN and baseline ≤ 2 ULN >3 ULN and baseline ≤ 3 ULN >5 ULN and baseline ≤ 5 ULN >10 ULN and baseline ≤ 10 ULN >20 ULN and baseline ≤ 20 ULN
AST	By distribution analysis: >2 ULN and baseline ≤ 2 ULN >3 ULN and baseline ≤ 3 ULN >5 ULN and baseline ≤ 5 ULN >10 ULN and baseline ≤ 10 ULN >20 ULN and baseline ≤ 20 ULN
Alkaline Phosphatase	> 1.5 ULN and baseline ≤ 1.5 ULN
Total Bilirubin	> 1.5 ULN and baseline ≤ 1.5 ULN > 2 ULN and baseline ≤ 2 ULN
Conjugated bilirubin	> 35% total bilirubin (when total bilirubin >1.5 ULN)
ALT and Total Bilirubin	ALT > 3 ULN and Total Bilirubin > 2 ULN and baseline ALT ≤ 3 ULN or Total bilirubin ≤ 2 ULN
CPK	> 3 ULN and ≤ 5 ULN and baseline ≤ 3ULN >5 ULN and ≤ 10 ULN and baseline ≤ 5 ULN >10 ULN and baseline ≤ 10 ULN
Creatinine	≥ 150 μmol/L (adults) ≥ 30% from baseline ≥ 100% from baseline
CLcr (mL/min) (Estimated creatinine clearance based on the Cockcroft-Gault equation)	≥15 - <30 (severe decrease in GFR) ≥30 - < 60 (moderate decrease in GFR) ≥60 - <90 (mild decrease in GFR) ≥ 90 (normal GFR)
eGFR (mL/min/1.73m2) (Estimate of GFR based on an MDRD equation)	≥15 - <30 (severe decrease in GFR) ≥30 - < 60 (moderate decrease in GFR) ≥60 - <90 (mild decrease in GFR) ≥ 90 (normal GFR)

Parameter	PCSV
Uric Acid Hyperuricemia: Hypouricemia:	>408 µmol/L <120 µmol/L
Blood Urea Nitrogen	≥17 mmol/L
Chloride	<80 mmol/L >115 mmol/L
Sodium	≤129 mmol/L ≥ 160 mmol/L
Potassium	< 3 mmol/L ≥ 5.5 mmol/L
Glucose Hypoglycaemia Hyperglycaemia	≤ 3.9 mmol/L and < LLN ≥ 7 mmol/L (fasted); ≥ 11.1 mmol/L (unfasted)
HbA1c	>8%
Albumin	≤25 g/L
Hs-CRP	> 2 ULN or >10 mg/L, if ULN not provided
Hematology	
WBC	< 3.0 Giga/L (3000/ mm ³) (Non-Black) < 2.0 Giga/L (2000/ mm ³) (Black) ≥16.0 Giga/L (16000/ mm ³)
Lymphocytes	>4.0 Giga/L
Neutrophils	< 1.5 Giga/L (1500/ mm ³) (Non-Black) < 1.0 Giga/L (1000/ mm ³) (Black)
Monocytes	>0.7 Giga/L
Eosinophils	> 0.5 Giga/L (500/ mm ³) or > ULN if ULN ≥ 0.5 Giga/L
Hemoglobin	≤115 g/L (Male); ≤95 g/L (Female) ≥185 g/L (Male); ≥165 g/L (Female) Decrease from Baseline ≥15 g/L Decrease from Baseline ≥20 g/L
Hematocrit	≤0.37 v/v (Male) ; ≤0.32 v/v (Female) ≥0.55 v/v (Male) ; ≥0.5 v/v (Female)
RBC	≥6 Tera/L

Parameter	PCSV
Platelets	< 100 Giga/L (100 000/mm ³) ≥700 Giga/L (700000/mm ³)
Urinalysis	
pH	≤4.6 ≥8
Vital signs	

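### The SAP's last-value HbA1c rule for new-onset diabetes goes beyond the protocol definition and lets cases drop out at later data cuts; its ALT/AST bands do not give the protocol's hepatic AESI count

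*SAP*

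**What the plan says.** **Diabetes, protocol.** Section 9.4.3 gives three routes to new-onset diabetes. The first is a diabetes TEAE, where only the choice of MedDRA terms is left to the SAP: "Type 1 or type 2 diabetes TEAE (grouping of MedDRA terms will be specified in the statistical analysis plan". The second is two or more HbA1c values of at least 6.5%, with one exception: "For patients with only a single measurement available during the TEAE period, a single value" at that level is enough. The third is two or more fasting glucose values of at least 126 mg/dL. There the protocol expressly rejects the last-only case: "For patients with several fasting glucose measurements but with only the last one" high, the patient does not qualify.

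**Diabetes, SAP.** Appendix 10.3, Table 2 keeps these routes and makes three additions:
- an HbA1c default: "For patients with several HbA1c measurements but only with the last one" at or above 6.5%, the patient qualifies;
- a new glucose-lowering medication as a qualifying event on its own;
- an entry gate: "No medical history of diabetes as specified in Cardiovascular History and Cardiovascular Risk Factors and Medical History CRF pages", together with baseline HbA1c below 6.5%.

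**Hepatic, protocol.** The item headed "Increase in ALT or AST" in 9.4.3 is met at 3 x ULN or more if baseline is below ULN, or at 2 x baseline or more if baseline is at or above ULN.

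**Hepatic, SAP.** Table 2 uses an SMQ, the PCSV criteria and an eDISH plot, with no e-CRF tick box. Appendix 10.4 sets the ALT and AST criteria "By distribution analysis": above 2, 3, 5, 10 and 20 x ULN, each with baseline no higher than the same multiple.

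**Links.** Protocol 10.4.4.1 refers the AESI summaries to 9.4.3. SAP 5.8.2 takes them from Appendix 10.3. SAP section 7 allows ongoing analyses and plans an adolescent interim once all adolescents have data through week 24.

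**The concern.** TEAEs and other safety variables are the primary endpoint, and the AESI tables are part of that evaluation. If an AESI row uses a different rule from the one that defines the event in the protocol, its count answers a different question, and nothing in the table shows the reader this.

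The HbA1c sentence adds a second difficulty. Which value is last depends on when the data are cut. A patient can be a case at one cut and not at the next without any data correction. With about 14 adolescents planned, one such reversal moves the adolescent percentage by 1/14, about 7 points.

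**Working it through.** The documents state no AESI count, so there is no figure to reproduce. The check compares the rules.

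**1. HbA1c rules on every sequence.** Write 1 for a post-baseline value of at least 6.5% and 0 otherwise, in time order. For sequences of one to four values:

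| Sequence | Protocol | SAP | SAP after one more normal value |
|---|---|---|---|
| 1 | yes | yes | no (1,0) |
| 0,1 | no | yes | no (0,1,0) |
| 0,0,1 | no | yes | no (0,0,1,0) |
| 0,0,0,1 | no | yes | no (0,0,0,1,0) |

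The two rules agree on all other sequences. Under the protocol rule the only yes-to-no change is from 1 to 1,0. Under the SAP rule a change is possible after any number of values.

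**2. A concrete path.** Protocol Table 3 schedules HbA1c at weeks 12 and 24, then at visits C and F. Suppose a patient has 6.0% at week 12 and 6.6% at week 24. The SAP counts the patient if the interim data end at week 24. A visit C value of 6.1% removes the patient, unless a diabetes TEAE, the glucose rule or the medication rule is met.

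**3. Size, on assumed values.** Assume near-threshold patients with true HbA1c of 6.2% or 6.3%, within-person SD 0.2 and independent measurements. None of these figures is in the documents. Then p = P(value at least 6.5%) = P(Z at least 1.5) = 0.067, or P(Z at least 1.0) = 0.159. With n values, last-only is p(1-p)^(n-1) and two or more is 1 - (1-p)^n - np(1-p)^(n-1).

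| n | Last-only, mean 6.2% / 6.3% | Two or more, mean 6.2% / 6.3% |
|---|---|---|
| 2 | 6.2% / 13.3% | 0.4% / 2.5% |
| 4 | 5.4% / 9.4% | 2.4% / 12.1% |
| 8 | 4.1% / 4.7% | 9.6% / 37.0% |
| 16 | 2.4% / 1.2% | 29.0% / 74.7% |

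At about one value every 12 weeks, n = 2 is week 24 and n = 16 is week 192, within the planned maximum of about 4 years. The last-only share is largest relative to the two-value share at the adolescent interim, and shrinks with follow-up.

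For a whole group of N patients at n = 2, the SAP's expected HbA1c count is N[p² + p(1-p)] = Np, against Np² under the protocol. With assumed p of 1%, 2% and 5%:
- 14 adolescents: 0.14, 0.28 and 0.70, against 0.00, 0.01 and 0.04;
- 120 patients: 1.20, 2.40 and 6.00, against 0.01, 0.05 and 0.30.

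**4. Hepatic rules (x ULN).**

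| Baseline to post | Protocol AESI | SAP row above 2 | SAP row above 3 |
|---|---|---|---|
| 1.2 to 2.5 | yes | yes | no |
| 0.8 to exactly 3.0 | yes | yes | no |
| 0.8 to 2.5 | no | yes | no |
| 2.8 to 3.1 | no | no | yes |

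Taken together, the rows capture almost everything. A rise from below 1 to at least 3 falls in the row above 2. A doubling from a baseline between 1 and 20 crosses one of the five cut-points, except from 1.0 to exactly 2.0. Doublings from above 20 also fall outside every row. The rows include many non-AESI changes as well, so neither a single row nor their union equals the protocol criterion.

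**The case against.** Much of the opposing case stands, and it limits the point.

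- A reader might infer that the SAP alone makes the diabetes count unstable and that returning to the protocol wording would cure it. It would not: the protocol also counts a sole high value, which a normal second value removes.
- A reader might see the SAP's refusal of a last-only glucose value as an inconsistency of its own. The protocol refuses it too.
- The last-value default follows the same reasoning as the sole-value default: a high value with nothing after it is counted. It adds possible cases and hides none.
- A reader might infer that the AESI tables cannot be reconciled with site reports. SAP 5.8.3 provides listings of laboratory values meeting PCSV criteria and of possible Hy's law cases, so patient-level reconciliation is possible. What is missing is the tabulated count.
- A reader might take the N/A under SAP 1.2.3 as a false declaration. That heading, "Modifications from the Statistical Section in the Final Protocol", concerns the protocol's statistical section, whereas the definitions are in 9.4.3. The cross-reference in protocol 10.4.4.1 makes the gap worth recording, but not a misstatement.
- The baseline gate largely makes the words new onset operational.
- The analyses are descriptive, and SAP section 7 says the results will not change study conduct.

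None of this removes the difference in rules. Protocol 9.4.3 leaves only the MedDRA grouping for diabetes to the SAP, not the HbA1c rule. The SAP cites Amendments 5A and 5B; the amendment log attributes its later AESI change to infusion reactions, so version lag does not evidently explain the gap.

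**Conclusion.** The point holds as a matter of alignment. The SAP's HbA1c rule differs from protocol 9.4.3 on last-only high values and on no other sequence. Reported counts may therefore differ from the protocol definition; with few events they could coincide. A last-only case can drop out at the next cut. The sole-measurement default in both documents allows this once, when the second value arrives, while the SAP sentence allows it at any later cut.

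For ALT and AST the loss is the protocol-defined count, not the cases: only edge values escape all the PCSV rows. The documents do not support a reading that hepatic cases are generally missed or that the safety tables are uninterpretable.

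The definitional findings need no assumption. The HbA1c percentages do: they rest on an assumed mean, SD and independence, apply only to near-threshold patients, and fall from 6.2% to 13.3% at two values to 1.2% to 2.4% at sixteen.

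**What to change.** 1. In SAP Table 2, count HbA1c-based new-onset diabetes by the two-value rule. Put patients with one unconfirmed high value on a separate row, marking whether it was the last of several or the sole measurement. Data corrections aside, the confirmed count then cannot fall between cuts. The protocol's HbA1c count is the confirmed patients plus the sole-measurement patients.
2. Beside the PCSV rows, add one derived ALT/AST flag that applies the protocol 9.4.3 criterion.
3. Record as departures from protocol 9.4.3 the new glucose-lowering medication criterion, the baseline HbA1c gate of below 6.5%, and the separate display of sole-measurement cases.

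The cost is SAP wording, one extra row and one derived flag, all from data already collected.

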12. PK sample collected in all patients. For patients undergoing apheresis, a PK sample should be collected immediately before the apheresis procedure. For patients undergoing plasma exchange, a PK sample should be collected immediately before and after the procedure. For patients who are not undergoing apheresis, the PK sample should be drawn before the dose of study drug.
13. After the week 24 visit, visits are in a strict sequence of A through F and should occur every 4 weeks. After visit F, the sequence repeats (visits A through F) until the end of treatment visit.
14. The end of treatment visit should occur 4 weeks post the last dose. Patients who prematurely discontinue from study drug should return to the clinic within 5 days if possible for end of treatment visit assessments. At this visit, WOCBP will be provided with urine pregnancy tests with instructions to test for pregnancy at home every 4 weeks after this visit and Q4W when phone visits are scheduled (weeks 8 and 16 post last dose). Urine pregnancy testing will be done during clinic visits at week 12, week 20, and week 24. Patients who upon their study completion, may continue to receive treatment outside of the clinical trial (such as through a CUP, EAP, or ISS/IST) and thereby may forgo the 24-week follow-up period of the study. The follow-up period was intended to be an off-drug follow-up. No off-drug follow-up period is required for these patients. In this situation, the patient's EOT will be their last study visit.

15. At weeks 8 and 16 of the follow-up period all patients will be contacted by phone to query LMT compliance, to inquire about AEs or changes to concomitant medications, confirm required contraception use, and remind patients of pregnancy reporting. Women of childbearing potential will report the results of their home pregnancy test. Patients who upon their study completion, may continue to receive treatment outside of the clinical trial (such as through a CUP, EAP, or ISS/IST) and thereby may forgo the 24-week follow-up period of the study. No off-drug follow-up period is required for these patients. In this situation, the patient's EOT will be their last study visit.
16. Should be collected at the baseline visit or at any study visit for patients who have not previously been enrolled in an evinacumab or alirocumab clinical study.
17. PK sample (including ANGPTL3) only for evinacumab-naïve adolescent patients.

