2.3. Study Plan

This study consists of 4 periods: a run-in period (for patients who may require HoFH genotyping, patients whose background medical LMT has not been stable prior to screening, or those whose apheresis settings and/or schedule have not been stable for at least 8 weeks prior to screening), a 2-week screening period, an open-label treatment period, and a 24-week follow-up period after the last dose of study drug (See [Figure 1](#) below)

Study duration will vary for each patient in this open-label study designed to evaluate the long-term safety and efficacy of evinacumab in patients with HoFH. It will range from months up to approximately 4 years, depending on conditions met in protocol Section 5.1, including IP regulatory approval.

Figure 1: Study Flow Diagram

- ¹. Patients who may require HoFH genotyping and patients whose background LMT/apheresis settings and/or schedule has not been stable prior to baseline (day 1) will enter an up to 10-week run-in period.
- ² All patients who are on a stable background LMT will enter a 2-week screening period except for those from a previous evinacumab study who completed an end of study visit within 7 days prior to the baseline/day 1 visit for this open-label study.
- ³. Patients who completed an end of study visit in a previous evinacumab study within 7 days of the baseline/day 1 visit for this open-label study do not have to undergo the screening visit and may enroll directly into this study. The EOS visit from the previous study can serve as the baseline/day 1 visit for this open-label study and overlapping assessments do not need to be repeated in this study. Only those assessments and procedures not done in the previous study must be conducted at the baseline visit. These specific assessments to be administered to all patients are identified in the Schedule of Events. The Study event table is presented in Appendix 10.5 in protocol.
- ⁴. Starting on day 1 (baseline), patients will receive evinacumab 15 mg/kg IV administered Q4W.
- ⁵. Patients will be followed for 24 weeks after receiving the last dose of study drug.

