4.8.1. Adverse Events Variables

The period of safety observation starts from the time when the patient gives informed consent and continues into the following periods:

- The PRE-TREATMENT period is defined from the day the ICF is signed to the day before the first dose of open-label study treatment administration.
- The open-label treatment-emergent adverse event (TEAE) period is defined from the day of the first open-label study treatment administration to the day of the last open-label study treatment administration + 168 days (24 weeks).
- The POST-TREATMENT period is defined from the day after the end of the TEAE period to the last study visit.

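### New-onset diabetes: the fasting-glucose criterion has no baseline glucose condition and accepts any two high values, so some patients whose glucose has not changed count as new cases

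*SAP*

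**What the plan says.** SAP Appendix 10.3, Table 2 labels the event as NOD in patients without diabetes at baseline. Two conditions apply before any arm: "No medical history of diabetes as specified in Cardiovascular History and Cardiovascular Risk Factors and Medical History CRF pages", and "AND Hb1Ac < 6.5% at baseline". One of four arms must then be met: HbA1c, fasting glucose, a MedDRA diabetes term, or a new glucose-lowering medication.

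The glucose arm asks for "At least 2 values of fasting glucose" at or above 126 mg/dL (7.0 mmol/L). A lone high value, or a high value that is only the last of several, "will NOT be considered and will NOT qualify the patient as NOD". There is no condition on baseline glucose, and the two values need not be consecutive or within any interval. The HbA1c arm states its time limit in the criterion itself ("during the TEAE period. NOTE: For patients with only a single measurement available during the TEAE period"). The glucose arm mentions that period only in its note.

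SAP 4.8.1 defines the TEAE period as running "from the day of the first open-label study treatment administration to the day of the last open-label study treatment administration + 168 days". SAP 2.3 says of study duration: "It will range from months up to approximately 4 years". The protocol's definition (Section 9.4.3) has the same two-value glucose rule and states no baseline condition. SAP 1.2.3 declares no modification from the protocol.

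**The concern.** The HbA1c arm is protected by a baseline condition on HbA1c, but the glucose arm has no baseline condition on glucose. Take a patient with no diabetes history, HbA1c 6.3% and baseline fasting glucose 130 mg/dL, with later values of 128 and 131. This patient passes both entry conditions and is classified as new onset although nothing changed.

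The second problem is accumulation. The note shows that an isolated high glucose was not meant to count. Over a long follow-up, though, two isolated values years apart satisfy the rule. A patient usually at 115 mg/dL with 126 at week 16 and 127 at week 184 is a case.

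NOD is a named adverse event of special interest in a single-arm study, so no control group can net out the misclassification. The false count also grows with follow-up.

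**Working it through.** The documents give no NOD rate or glucose distribution, so there is no stated figure to reproduce. Glucose levels and variability below are assumptions.

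**Number of tests.** Protocol Table 3 schedules blood chemistry at weeks 8, 16 and 24, then at visits B, D and F. On the cycle ("After the week 24 visit, visits are in a strict sequence of A through F and should occur every 4 weeks") these fall at weeks 32, 40 and 48, so the spacing stays at 8 weeks. Scheduled on-treatment values are 24/8 = 3, 48/8 = 6, 104/8 = 13 and 208/8 = 26.

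**Formulas.** Let p be the chance that one value reaches 126 mg/dL, with values independent around a stable level.

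- Any two of n: 1 - (1-p)^n - n p (1-p)^(n-1).
- With a baseline value below 126 also required: multiply by (1-p).
- Two consecutive values: start with a = 1, b = 0; at each test replace (a, b) by ((a+b)(1-p), a p); the probability after n tests is 1 - a - b.

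At p = 0.01 the any-two probability is 1 - 0.970299 - 0.029403 = 0.03% for n = 3 and 2.8% for n = 26. At p = 0.05 it is 0.7% and 37.6%.

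**Individual patients.** Example: usual glucose 115, within-patient SD 8, z = (126-115)/8 = 1.375, p = 0.085.

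| Usual glucose, SD (mg/dL) | p | Any two, n = 3 | Any two, n = 26 | n = 26, baseline <126 required | n = 26, consecutive |
|---|---|---|---|---|---|
| 100, 10 | 0.005 | <0.1% | 0.7% | 0.7% | 0.1% |
| 115, 6 | 0.033 | 0.3% | 21.5% | 20.8% | 2.7% |
| 115, 8 | 0.085 | 2.0% | 65.8% | 60.2% | 15.4% |
| 115, 10 | 0.136 | 5.0% | 88.5% | 76.5% | 34.1% |
| 130, 6 | 0.748 | 84.1% | about 100% | 25.2% | about 100% |
| 130, 8 | 0.691 | 77.3% | about 100% | 30.9% | about 100% |
| 130, 10 | 0.655 | 72.6% | about 100% | 34.5% | about 100% |

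The two weaknesses are separate. A baseline condition removes most patients who were already high but hardly changes the borderline result. A consecutive rule does the reverse.

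**Whole cohort.** I averaged the same formulas over a normal distribution of usual glucose, from mean 90, SD 10 to mean 95, SD 12 mg/dL, with within-patient SD equal to 6% of the usual level.

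| Tests | Flagged, present rule | Present rule minus both changes, per 120 patients |
|---|---|---|
| 3 | 0.1-0.8% | at most about 0.6 |
| 13 | 0.4-3.2% | 0.3-2.5 |
| 26 | 0.7-4.8% | 0.6-3.8 |

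At 26 tests the flagged share is 0.6-3.8% with the baseline condition alone and 0.2-1.7% with both changes. In patients, 0.7-4.8% of 120 is about 1 to 6. This calculation does not apply the history and HbA1c conditions, which would remove some of those flagged.

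**The case against.** **Such cases are visible elsewhere.** SAP 10.4 sets the fasted-glucose PCSV at 7 mmol/L, the same cut-off. SAP 5.8.3 tabulates PCSVs by normal/missing versus abnormal baseline and lists the patients. The patient with baseline 130 appears there as abnormal at baseline, and HbA1c is summarised by visit. This stands as mitigation, but it does not change who is counted as NOD.

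**Over-inclusion is a legitimate safety stance.** The SAP resolves doubt conservatively elsewhere: missing severity becomes severe, missing causality becomes related, and unclear onset becomes treatment-emergent. The two-value rule is also the protocol's own. This stands against replacing the rule with a consecutive one, which would trade sensitivity for specificity. It does not justify calling a glucose level that was already present new.

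**The effect is small and nothing is tested.** This also stands. Four years is the maximum duration, not the typical one. The planned adolescent analysis at week 24 has 3 scheduled values.

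**Stronger readings.** A reader might infer that pre-existing diabetes in general is counted as new. The documents do not support this, because known diabetes and baseline HbA1c of 6.5% or more are excluded before the glucose arm applies. A reader might also take the 21-89% figures for a usual glucose of 115 as the inflation of the study's NOD rate. They describe one assumed type of borderline patient with 26 tests; at a usual level of 100 the figure is at most 0.7%.

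**Conclusion.** The point holds in limited form. The glucose arm misclassifies patients who enter with undiagnosed or HbA1c-discordant high glucose, and it increasingly flags stable borderline patients as tests accumulate. This follows from the stated rule and does not depend on the simulated sizes.

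Under the assumed distributions, the present rule flags about 0.1-0.8% of patients at 3 tests and 0.7-4.8% if everyone had 26. Those figures assume independent values around a stable level; correlated values would change them. The documents do not show how many patients have discordant or borderline glucose. The consequence is a descriptive count that may be a few patients too high, with no comparator to reveal it. The adolescent 24-week analysis is barely affected.

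Two ambiguities should be settled at the same time. The TEAE period starts on the first dosing day, when samples are drawn before dosing, so a pre-dose Day 1 value could be read as one of the two. For R1500-CL-1629 rollovers, SAP 6.1 takes baseline from before the parent study's double-blind dosing, so the entry condition may be well out of date when the patient enters this study.

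**What to change.** In the glucose row of SAP Table 2:

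- Count only post-dose fasting values within the TEAE period.
- Require baseline fasting glucose below 126 mg/dL, and state which baseline applies to R1500-CL-1629 rollovers.
- List separately the patients who meet only the present rule.
- Add a supplementary count requiring two consecutive fasting values of at least 126 mg/dL. Keep the protocol's two-value rule for the main count.
- Declare the change from Protocol 9.4.3 in SAP 1.2.3.

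The cost is one table row, a declaration, one listing, one extra count and a small program change. A few true cases with a single high baseline glucose would move to the listing; the HbA1c, adverse-event-term and medication arms can still capture them. The baseline condition is not complete protection: at a stable 130 mg/dL, 25-35% of patients would still pass it by chance.
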